### **6.3 Planned Study Visits**

The second study product injection will be administered at Visit 05, Day 29 (window  $\pm$  3 days).

The third study product injection will be administered at Visit 08, Day 57 (window  $\pm$  3 days) for subjects in Groups A, B, D, and E and will be administered at Visit 09, Day 180 for Group C.

At the Second and Third Vaccination Visits, prior to the study product injection:

- For a subject to receive the study product injection, Individual Halting Criteria will be reviewed (refer to [Section 8.6.2](#)).
- Interim medical history, including an assessment for new medical conditions, stability of chronic diseases, and symptoms suggestive of a MAAE/NOCMC/PIMMC, will be obtained by interview of subjects and any changes since the previous clinic visit or contact will be noted.
- All concomitant medications will be recorded on the appropriate eCRF, if known and not previously collected.
- All newly identified AEs/SAEs/MAAEs/NOCMCs/PIMMCs will be recorded on the appropriate eCRF.
- Vital signs, including oral temperature, pulse, and blood pressure, will be obtained prior to the study product injection. Subjects must not eat or drink anything hot or cold, or smoke within 10 minutes prior to taking oral temperature.
- A targeted physical examination, including an assessment for signs suggestive of a MAAE/NOCMC/PIMMC, may be performed, if indicated based on review of interim medical history, by a study clinician licensed to make medical diagnoses and listed on the Form FDA 1572 as the site PI or sub-investigator.

---

- For women of childbearing potential, contraceptive methods will be reviewed to ensure eligibility, recent menstrual history will be obtained, pregnancy avoidance counseling will be provided, and a urine pregnancy test will be performed. A test performed on a sample obtained within 24 hours prior to vaccination must be negative.
- Pre-administration reactogenicity assessments will be performed to establish baseline.
- Venous blood samples will be obtained for clinical safety labs, PBMC isolation, and immunologic assays, in volumes as specified in Table 8, for Groups A, B, D, and E, and Table 9 for Group C. The clinical safety laboratory results will not be available or reviewed prior to study vaccination.

Subjects will then receive a single dose of study product via IM injection into the deltoid muscle of the preferred arm.

- The second or third study product injections may be given in the same arm as the previous study product injection as long as there is no interference with the reactogenicity assessment. The site of injection (right or left arm) and time of administration will be recorded on the appropriate eCRF. Subjects will be observed in the clinic for at least 30 minutes after the study vaccination. The injection site will be examined, post-administration reactogenicity assessments will be performed, and any AE/SAEs will be recorded on the appropriate eCRF prior to discharge from the clinic.
- Subjects will be provided with an e-Memory Aid or Paper Memory Aid and thermometer for recording daily maximum oral temperature, solicited injection site and systemic reactions, unsolicited AEs, and concomitant medications, beginning on the evening of the day of study product injection and continuing daily for the next seven days. Subjects will be encouraged to take their temperature around the same time each day and also if they feel feverish. Subjects will be instructed on how to use the memory aid and how to rate any AEs.
- Subjects will be instructed to notify the study center if they develop any severe reactions and/or fever equal to or exceeding 38°C (100.4°F). If the investigator deems the reaction warrants further evaluation or intervention, the investigator will give further instructions on the proper course of action, including a return to the clinic for immediate evaluation if appropriate.

### **6.3.1 Follow-up**

Follow up visits are scheduled as indicated in the Schedule of Events, Table 8 for Groups A, B, D, and E, and Table 9 for Group C. Subjects will be followed for one year after their last study vaccination.

### 6.3.2 Early Termination Visit

The following activities will be performed at the early termination visit on subjects who withdraw, or are withdrawn or terminated from this trial and who are willing to participate in the visit, clinical evaluations, and study procedures:

- Interim medical history, including an assessment for new medical conditions and symptoms suggestive of a MAAE/NOCMC/PIMMC, will be obtained by interview of subjects and any changes since the previous clinic visit or contact will be noted.
- Memory Aid information will be reviewed with subjects (if within 7 days after the last study vaccination).
- All concomitant medications will be recorded on the appropriate eCRF (if within 28 days after the last study product injection).
- AEs will be assessed and recorded as described in [Section 3.1](#).
- Vital signs, including oral temperature, pulse, and blood pressure, may be obtained if clinically indicated.
- A targeted physical examination, including an assessment for signs suggestive of a MAAE/NOCMC/PIMMC, may be performed, if indicated based on review of interim medical history, by a study clinician licensed to make medical diagnoses and listed on the Form FDA 1572 as the site PI or sub-investigator.
- The study vaccination site will be examined (if within seven days after the last study product injection).
- Post-administration reactogenicity assessments will be performed (if within seven days after the last study product injection).
- Approximately 8.5 mL of venous blood will be collected for serum antibody assays (if within 28 days after the last study vaccination).
- Approximately 7 mL of venous blood will be collected for clinical safety labs (WBC, hemoglobin, platelets, ALT, and creatinine), and performed by the clinical laboratory if within 28 days after the last study vaccination.

---

## **6.4 Unscheduled Study Visits (if needed)**

Participants may be asked to come in for additional clinic visits if, for example, the need arises for follow-up of local or systemic AE such as febrile illnesses, or for requests for repeat blood draws for scheduled laboratory testing from the clinical laboratory due to sample hemolysis or clotting.

A supplemental visit eCRF will be filled and signed by the appropriate personnel. All unscheduled visits will be entered into Emmes' Advantage eClinical® internet data entry system on the appropriate eCRFs. Please see the MOP for details.

## **6.5 Protocol Deviations**

A protocol deviation is any noncompliance with the clinical trial protocol, GCP, or protocol-specific MOP requirements. The noncompliance may be either on the part of the subject, the investigator, or the study site staff. As a result of deviations, corrective actions should be developed by the site and implemented promptly. It is the responsibility of the site PI and other study personnel to use continuous vigilance to identify and report protocol deviations. All individual protocol deviations will be addressed in subject study records. All protocol deviations, either individual, product, or site-specific will be collected and the record stored in a sponsor-determined location. Protocol deviations must be sent to the IRB per its guidelines. The site PI and other study personnel are responsible for knowing and adhering to their IRB requirements.

---

## 7 DESCRIPTION OF CLINICAL AND LABORATORY EVALUATIONS

### 7.1 Clinical Evaluations

Complete medical history will be obtained by interview of subjects at the screening visit. Subjects will be queried regarding a history of significant medical disorders of the head, eyes, ears, nose, throat, mouth, cardiovascular system, lungs, gastrointestinal tract, liver, pancreas, kidney, urologic system, nervous system, blood, lymph nodes, endocrine system, musculoskeletal system, skin, and genital/reproductive tract. A history of any allergies, cancer, immunodeficiency, psychiatric illness, substance abuse, and autoimmune disease will be solicited. At follow-up visits after the first study vaccination, an interim medical history will be obtained by interview of subjects noting any changes since the previous clinic visit or contact. The interim medical history should include an assessment for new medical conditions and symptoms suggestive of a MAAE/NOCMC/PIMMC.

Concomitant medications will be collected as described in [Section 7.1.1](#).

At the screening visit a physical examination will be performed on all subjects as described in [Section 6.1](#). At subsequent clinic visits, a targeted physical examination may be performed, if indicated based on the subject's interim medical history, by a study clinician licensed to make medical diagnoses and listed on the Form FDA 1572 as the site PI or sub-investigator. Targeted physical examinations should also include an assessment for signs suggestive of a MAAE/NOCMC/PIMMC.

Vital signs (oral temperature, pulse, and blood pressure) will be collected at the screening visit, at vaccination visits, and at clinic visits scheduled within 7 days after a vaccination. At other visits, vital signs will be assessed if clinically indicated. Vital signs assessed on Day 1 prior to the first study product injection will be considered as baseline. Subjects must not eat or drink anything hot or cold, or smoke within 10 minutes prior to taking oral temperature. Height and weight will be collected at the screening visit for the calculation of BMI.

Reactogenicity assessments will include an assessment of solicited AEs occurring from the time of each study product injection through seven days after each study product injection, which includes an assessment of injection site reactions including pruritus, erythema, induration/swelling, pain, and tenderness as well as systemic reactions including fever, chills, fatigue, malaise, myalgia, arthralgia, headache, and nausea or vomiting. Pre-administration

---

reactogenicity assessments will be performed to establish baseline, then the study product injection will be given.

Subjects will be observed in the clinic for at least 30 minutes after each study vaccination. The injection site will be examined, post-administration reactogenicity assessments will be performed, and any AE/SAEs will be recorded on the appropriate eCRF prior to discharge from the clinic. The injection site will also be examined approximately 7 days after each study product injection.

All subjects will complete a Memory Aid from the time of each study product injection through 7 days after each study product injection. Subject Memory Aids will be reviewed with the subjects for AEs (solicited injection site and systemic reactions and unsolicited AEs) during each post-injection clinic or phone visit through 7 days after the injection.

### **7.1.1 Assessment of Concomitant Medications/Treatments other than Study Product**

Administration of any medications, therapies, or vaccines will be recorded on the appropriate eCRF. Concomitant medications will include all current medications and medications taken in the 60 days prior to the first vaccination and those taken from the time of vaccination through approximately 28 days after each vaccination, as described in [Section 3.1](#). Medications reported in the electronic case report form (eCRF) are limited to those taken within 30 days prior to the first study product injection and those taken in the 28-day post-vaccination interval. Prescription and over-the-counter drugs will be included as well as herbals, vitamins, and supplements. In addition, receipt of non-study vaccines will be solicited from the time of each vaccination through approximately 28 days after each vaccination and reported in the eCRF. Use of a new medication should prompt evaluation for the occurrence of any MAAE, including a NOCMC.

Medications that might interfere with the evaluation of the investigational product(s) should not be used during the trial-reporting period (approximately 12 months after the last study vaccination) unless clinically indicated as part of the subject's health care. Medications in this category include the prohibited medications per the Subject Exclusion Criteria (see [Section 5.1.2](#)). In addition, the site PI or appropriate sub-investigator may identify other medications that should not be used due to a risk to subject safety or assessment of reactogenicity and immunogenicity.

---

## 7.2      **Laboratory Evaluations**

### 7.2.1      **Clinical Laboratory Evaluations**

Subjects will be screened for HIV-1 and HIV-2 infection by a fourth-generation testing algorithm, for HCV infection, and for HBsAg. Screening labs also include WBC, hemoglobin, platelets, creatinine, and ALT.

Serum (screening visit) and urine (study product injection visits) pregnancy tests will be performed. Serum pregnancy tests will be performed by the Quest clinical diagnostic laboratory. Urine pregnancy CLIA-waved tests will be performed by research staff at the research site specimen processing laboratory. Pregnancy testing will be done at the screening visit and within 24 hours prior to each study product injection on all women of childbearing potential. Results must be negative and known prior to enrollment on Day 1 and administration of each study product injection.

Clinical safety laboratory parameters (WBC, hemoglobin, platelets, ALT, and creatinine) will be collected from each subject on the day of and prior to each study product injection, approximately 7 days after each study product injection, and approximately 28 days after each study product injection (which may also serve as the clinical safety laboratory samples for the second and/or third study product injection). These evaluations will be performed by the Quest laboratory. Venous blood samples will be collected for these safety labs. The results from the clinical safety laboratory parameters collected on the day of study product injections will not be available or reviewed prior to study product injection.

Laboratory values that are outside the range of eligibility but are thought to be due to an acute condition or due to laboratory error may be repeated once. One or more of the laboratory parameters may be repeated at any time during the study as determined by the PI, if indicated by an AE. A clinically significant abnormal value should be repeated within 10 days if possible and followed up as clinically relevant.

The volume of venous blood to be collected for the clinical safety laboratory evaluations is presented in Table 8 and Table 9.

### 7.2.2      **Research Assays**

The research assays to be performed for the immunologic endpoints are specified below.

### **7.2.2.1 ELISA (anti Sm-p80 IgG)**

Vaccine-specific IgG antibody responses will be assessed by ELISA using serum collected from subjects (8.5 ml of blood collected in a serum separator tube) at specific time points selected to evaluate the kinetics of the response after each administration, peak response, and durability, including prior to each vaccination on the day of vaccination, at 7 and 28 days after each vaccination, and at 124 days after the last vaccination. The 28-day post-vaccination sample also serves as the day of vaccination sample for a subsequent vaccination given at a 28-day interval.

This volume is sufficient to provide 1 primary and 1 backup sample for analysis. The goal will be to compare the serum IgG titers at each time point among participants who received an Sm-p80 study product across treatment groups. Endpoint titer ELISAs will be performed by SCRI as follows. Titers of total IgG will be measured against the Sm-p80 protein. Briefly, thawed serum samples are serially diluted (12 dilutions at 4-fold each) using robotic liquid handlers on duplicate 384-well plates. The serially diluted sera are transferred and incubated on ELISA plates coated with Sm-p80 protein. Appropriate standards (pooled participant sera) and controls will be included for plate quality control based on criteria established during prior optimizations. Following, secondary antibody (HRP-conjugated) incubation, plates will be developed and read at OD 450-570nm. Endpoint titer will be calculated for each curve and duplicates will be averaged if within established variance limits.

### **7.2.2.2 RNA-Seq**

RNA Sequencing (RNA-Seq) will be performed by Novogene from the whole blood PAXgene tubes that will be shipped from TTUHSC. Novogene will perform total RNA extraction, RNA quantification and qualification, library preparation, Illumina whole-transcriptome sequencing, and raw data quality checking. Novogene will transfer the raw FASTQ files to Emmes. Emmes will perform RNA-Seq data analyses, including pre-alignment sequence quality control, reference alignment, post-alignment quality control, gene expression quantification, differential gene expression analyses, gene cluster and pathway analyses, as well as predictive modeling (see Section 10.5.4).

### **7.2.2.3 Laboratory Specimen Preparation, Handling, and Storage**

Instructions for specimen preparation, handling, and storage are included in the laboratory manual and protocol-specific MOP as appropriate.

### **7.2.2.4 Laboratory Specimen Shipping**

Specimens collected during the study will be shipped according to the study MOP. Specimen labeling requirements will also be included in the study MOP.

---

## 8 ASSESSMENT OF SAFETY

### 8.1 Assessing and Recording Safety Parameters

Safety will be assessed by the frequency and severity of:

1. SAEs occurring from the time of the first study product injection through the end of follow-up which is approximately 12 months after the last study product injection.
2. Solicited AEs – reactogenicity events occurring from the time of each study product injection through 7 days after each study product injection:
  - a) Injection site reactions including pruritus, erythema, induration/swelling, pain, and tenderness.
  - b) Systemic reactions including fever, chills, fatigue, malaise, myalgia, arthralgia, headache, nausea, and vomiting.
3. Clinical safety laboratory AEs assessed as described in [Section 7.2.1](#). Parameters to be evaluated include WBC, hemoglobin, platelets, ALT, and creatinine.
4. Unsolicited AEs – non-serious AEs occurring from the time of each study product injection through 28 days after the study product injection.
5. MAAEs, NOCMCs, and PIMMCs occurring from the time of the first study product injection through the end of follow-up which is approximately 12 months after the last study product injection.

#### 8.1.1 Adverse Events (AEs)

The International Conference on Harmonisation (ICH) E6 defines an AE as any untoward medical occurrence in a patient or clinical investigation subject administered a pharmaceutical product regardless of its causal relationship to the study treatment. The FDA defines an AE as any untoward medical occurrence associated with the use of a drug in humans, whether or not considered drug related.

An AE can therefore be any unfavorable and unintended sign (including an abnormal laboratory finding), symptom, or disease temporally associated with the use of medicinal (investigational) product. The occurrence of an AE may come to the attention of study personnel during study

---

visits and interviews of a study recipient presenting for medical care, or upon review by a study monitor.

All AEs, including solicited local (injection site) and systemic (subjective and quantitative) reactions, will be captured on the appropriate eCRF. Information to be collected for AEs includes event description, date of onset, assessment of severity, relationship to study product and alternate etiology (assessed only by those with the training and authority to make a diagnosis and listed on the Form FDA 1572 as an investigator), date of resolution, seriousness and outcome. AEs occurring during the trial collection and reporting period will be documented appropriately regardless of relationship. AEs will be followed through resolution.

Any medical condition that is present at the time that the subject is screened will be considered as baseline and not reported as an AE. However, if the severity of any pre-existing medical condition increases, it should be recorded as an AE.

If an event meets both the criteria of a study endpoint and an AE, the event will be reported either as a study endpoint or as an AE (not both).

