23. Positive serologic test for hepatitis B surface antigen (HBsAg).

24. Positive confirmatory test for hepatitis C virus (HCV) infection.

25. Acute febrile illness (oral temperature  $\geq 38^{\circ}\text{C}$ ) or other acute illness within three days prior to study product injection.\*

\*Note for afebrile, acute illness only: If a subject is afebrile, his/her acute illness is nearly resolved with only minor residual symptoms remaining, and, in the opinion of the site PI or appropriate sub-investigator, the residual symptoms will not interfere with the ability to assess safety parameters as required by the protocol, the subject may receive study product injection without further approval from the DMID Medical Officer.

26. Not willing to avoid donating blood during the study.

27. Has any condition that would, in the opinion of the site investigator, place the subject at an unacceptable risk of injury or render the subject unable to meet the requirements of the protocol.

---

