### 6.1 Screening, Visit 00 (Day -30 to Day -1)

All subjects will have a screening visit in the 30 days prior to their first study product injection visit. Screening laboratory evaluations with abnormal values may be repeated during this period only as specified in [Section 7.2.1](#).

Subjects who are not enrolled within the 30-day window after the screening visit may be rescreened to refresh the window.

Written informed consent will be obtained prior to conducting any screening procedures. A single consent form will be used to document consent to screening and to participation in the study.

The following procedures will be performed at the initial screening visit (Table 7):

- Subjects will be provided with a description of this trial (purpose and study procedures) and asked to read and sign the ICF. The ICF will be signed prior to performing any study procedures, including any screening procedures.
- Demographic information will be obtained by interview of subjects.
- Eligibility criteria will be reviewed with subjects and eligibility assessed by review of the inclusion and exclusion criteria.
- A complete medical history will be obtained and all concomitant medications taken in the prior 60 days will be identified in order to determine the stability of chronic diseases and eligibility. Medications reported in the eCRF are limited to those taken within 30 days prior to the first study vaccination.
- Vital signs, including oral temperature, blood pressure, and pulse, will be obtained to ensure eligibility. Subjects must not eat or drink anything hot or cold, or smoke, within 10 minutes prior to oral temperature measurement.
- Height and weight will be obtained to calculate BMI.

---

- A physical examination that assesses general appearance and the following areas/systems: skin, lymph nodes, HEENT (head, ears, eyes, nose, and throat), neck, cardiovascular, pulmonary, abdomen, extremities, musculoskeletal, and neurological, will be performed by a study clinician licensed to make medical diagnoses and listed on the Form FDA 1572 as the site PI or sub-investigator.
- Venous blood will be collected for screening laboratory tests (WBC, hemoglobin, platelets, creatinine, ALT, HIV-1/HIV-2 testing, anti-HCV antibody, HBsAg, and pregnancy test for female subjects of childbearing potential) in volumes as specified in Table 7.
- HIV test counseling will be provided.

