9. SAFETY EVALUATION

All safety analyses will be presented using the safety population. Subjects will be grouped for summary statistics using treatment group. An additional “All Subjects” group will be included to summarize across groups for solicited and unsolicited AE exhibits.

Any medical condition that is present at the time that the subject is screened will be considered baseline and not reported as an AE, unless it worsens in severity or increases in frequency during the study.

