[Systemic Symptom 2]	None																			

Table 25: Number and Percentage of Subjects Experiencing Solicited Events by Symptom, Maximum Severity and Treatment Group – Post Dose 1
(Continued)

Symptom	Severity	Group A: 100 µg Sm-p80 (unadjuvanted) (N=X)			Group B: 10 µg Sm-p80 + 5 µg GLA-SE (N=X)			Group C: 30 µg Sm-p80 + 5 µg GLA-SE (delayed booster) (N=X)			Group D: 30 µg Sm-p80 + 5 µg GLA-SE (N=X)			Group E: 100 µg Sm-p80 + 5 µg GLA-SE (N=X)			All Subjects (N = X)			
		n	%	95% CI ^a	n	%	95% CI ^a	n	%	95% CI ^a	n	%	95% CI ^a	n	%	95% CI ^a	n	%	95% CI ^a	
	Mild																			
	Moderate																			
	Severe																			
Injection Site Symptoms																				
Any Injection Site Symptom	None	x	xx	x.x, x.x	x	xx	x.x, x.x	x	xx	x.x, x.x	x	xx	x.x, x.x	x	xx	x.x, x.x	x	xx	x.x, x.x	
	Mild																			
	Moderate																			
	Severe																			
[Injection Site Symptom 1]	None																			
	Mild																			
	Moderate																			
	Severe																			
[Injection Site Symptom 2]	None																			
	Mild																			
	Moderate																			
	Severe																			

Table 25: Number and Percentage of Subjects Experiencing Solicited Events by Symptom, Maximum Severity and Treatment Group – Post Dose 1
(Continued)

Symptom	Severity	Group A: 100 µg Sm-p80 (unadjuvanted) (N=X)				Group B: 10 µg Sm-p80 + 5 µg GLA-SE (N=X)				Group C: 30 µg Sm-p80 + 5 µg GLA-SE (delayed booster) (N=X)				Group D: 30 µg Sm-p80 + 5 µg GLA-SE (N=X)				Group E: 100 µg Sm-p80 + 5 µg GLA-SE (N=X)				All Subjects (N = X)			
		n	%	95% CI ^a	n	%	95% CI ^a	n	%	95% CI ^a	n	%	95% CI ^a	n	%	95% CI ^a	n	%	95% CI ^a	n	%	95% CI ^a			
Note: N = Number of subjects in the Safety Population who received the specified dose. Severity is the maximum severity reported over all solicited symptoms post dosing for each subject.																									
^a 95% confidence intervals are from the Wilson score method without continuity correction.																									

Tables with similar format to [Table 25](#):**Table 26: Number and Percentage of Subjects Experiencing Solicited Events by Symptom, Maximum Severity, and Treatment Group – Post Dose 2****Table 27: Number and Percentage of Subjects Experiencing Solicited Events by Symptom, Maximum Severity, and Treatment Group – Post Dose 3****Table 28: Number and Percentage of Subjects Experiencing Solicited Events by Symptom, Maximum Severity, and Treatment Group – Post Any Dose**

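### Pre-dose symptom scores do not enter the solicited-event definition, so a symptom unchanged by a dose is still counted; the AE baseline wording also leaves a gap between screening and dose 1

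*Protocol*

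**What the plan says.** **Solicited symptoms.** Protocol 6.2 requires a symptom assessment before dose 1 as a baseline, and Protocol 6.3 says the same for doses 2 and 3: "Pre-administration reactogenicity assessments will be performed to establish baseline". SAP 3.3 names a single reactogenicity baseline, on Day 1 before the first injection.

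SAP 9.3.1 then summarises the proportion with at least one solicited event, and the maximum severity in the 7 days after each vaccination. The note to Table 25, whose format Tables 26–28 follow, reads: "Severity is the maximum severity reported over all solicited symptoms post dosing for each subject". The pre-dose score has no part in either rule. It does appear in the Pre-Dose column of Table 29 and the tables built on it (30–43), and in Listings 10 and 11.

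**Blood pressure.** Protocol 8.5 and Appendix C do adjust for baseline. A subject who starts at Grade 1 has an AE only if a later value reaches a higher grade.

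**Other AEs.** Protocol 8.1.1 says "Any medical condition that is present at the time that the subject is screened will be considered as baseline", and SAP 3.3 and SAP 9 repeat the screening reference. Protocol 6.1 gives the timing: "All subjects will have a screening visit in the 30 days prior to their first study product injection visit". Protocol 8.1.1 and SAP 3.3 make a pre-existing condition an AE when its severity increases. SAP 9 adds frequency: "unless it worsens in severity or increases in frequency during the study".

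**The concern.** Solicited reactions and unsolicited AEs are both primary endpoints (Protocol 3.3.1). A baseline score that is collected before every injection but plays no part in deciding what counts as an event cannot separate a new symptom from one the subject already had. A mild headache present before the injection and still mild the next day is tabulated as a post-vaccination event. In groups of nine, one such subject visibly changes the reported rate and the group differences in Table 24.

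Some symptomatic subjects can be dosed. The note to exclusion criterion 25 allows injection of an afebrile subject when "his/her acute illness is nearly resolved with only minor residual symptoms remaining", and Protocol 8.6.2 repeats that exception for later doses.

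The screening wording raises a second, smaller question: how to classify a condition that begins after screening but before dose 1.

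**Working it through.** **Inputs.** Nine subjects per group and three injections (Protocol 3.1). Up to 30 days from screening to dose 1 (Protocol 6.1). The proportion q of subjects with a solicited symptom at a pre-injection assessment that persists unchanged afterwards is not in the documents. I assume 2%, 5% and 10%.

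**1. The plan's own figure.** Protocol 10.2 and SAP Table 4 use 1 − (1 − p)^n. For p = 0.20 and n = 9, 1 − 0.8^9 = 0.866, as stated. The point does not depend on this figure, but the same formula is used below.

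**2. Weight of one subject.** 1/9 = 11.1 percentage points.

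**3. Subjects counted when the vaccine causes nothing.** For one dose, the expected count is 9q and the chance of at least one is 1 − (1 − q)^9. Over three doses, if independent, Q = 1 − (1 − q)^3, the expected count is 9Q and the chance of at least one is 1 − (1 − Q)^9.

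| q (assumed) | 9q, one dose | P(≥1), one dose | Q | 9Q, any dose | P(≥1), any dose |
|---|---|---|---|---|---|
| 2% | 0.18 | 0.17 | 0.059 | 0.53 | 0.42 |
| 5% | 0.45 | 0.37 | 0.143 | 1.28 | 0.75 |
| 10% | 0.90 | 0.61 | 0.271 | 2.44 | 0.94 |

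If the same subjects have the symptom each time, as with a chronic complaint, the any-dose count falls towards the one-dose column.

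**4. When the vaccine does cause reactions.** With a vaccine-caused rate t, independent of the background, the observed one-dose rate is 1 − (1 − t)(1 − q). For t = 0.20 and q = 0.10 this is 1 − 0.8 × 0.9 = 0.28, an excess of 8 points rather than 10, because some of these subjects would have been counted anyway. The difference between two groups with the same background is (t₁ − t₂)(1 − q). The background adds noise and shrinks a real difference somewhat, but it does not create one on average.

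**5. Can the planned displays recover the information?** Tables 29–43 give group counts by day and do not link a subject's pre-dose and post-dose grades. Listings 10 and 11 would allow matching by hand. Listing 10 records alternate etiology for Grade 3 events only, so it gives no such attribution for mild or moderate symptoms.

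**6. Is a pre-dose score available for every symptom?** SAP 9.3.1 names only systemic symptoms as collected before vaccination. Table 29 has Pre-Dose cells for systemic and injection-site symptoms alike.

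**7. Onset between screening and dose 1.** Such a condition is not baseline under Protocol 8.1.1. Nor is it clearly an AE: Protocol 8.1 restricts unsolicited AEs to those occurring from the injection onwards, and onset dates are recorded. Protocol 8.1.1.1 tells sites to report when in doubt. The documents therefore do not settle its status.

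**The case against.** The strongest reply is that counting every post-dose symptom is the primary endpoint as written, and is the cautious choice in a first-in-human trial. A count restricted to grades above the pre-dose score could miss a vaccine reaction that recurs, or prolongs an existing complaint, at the same grade. That stands, and it is why the existing tables should remain and the new count should sit beside them rather than replace them.

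The exclusion and deferral rules also matter. Criterion 25 excludes acute illness within three days before injection. Protocol 8.6.2 defers injection for signs, symptoms or illness on the day. The exceptions are limited to afebrile, nearly resolved illness judged not to interfere with safety assessment. Most acute illness is removed, leaving mainly minor residual, chronic or intermittent complaints.

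Four stronger readings are tempting but not supported:

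- *That the pre-dose scores are unused.* They are tabulated by day and listed. They are absent only from the event definition.
- *That illness starting before dose 1 is counted as an unsolicited AE.* Nothing says so. The window and the recorded onset date point the other way, Protocol 6.2 reviews medical history before dosing, and Listing 7 gives condition start days. The defect is an unassigned interval.
- *That the frequency rule in SAP 9 cannot be applied.* Protocol 8.1.1.1 requires onset and duration for each episode of an intermittent AE, so this goes too far. The two worsening rules still differ.
- *That Table 24 is biased towards one group.* Background symptoms unrelated to dose give no such expectation.

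**Conclusion.** The point holds for solicited events. The plan collects a pre-injection score at each dose and calls it baseline, but Tables 20–28 and Table 24 do not use it to decide whether a symptom is new or worse. For blood pressure the plan already applies the principle.

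The size cannot be derived from the documents. At an assumed 2% to 10% per injection, the range is about 0.5 to 2.4 of 9 subjects per group over three doses. That is an upper figure: it takes doses as independent, symptoms as persisting unchanged, and no subject as otherwise having an event. The exclusion and deferral rules reduce it further. One subject is 11 points.

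The baseline and worsening wording is a separate and smaller matter of consistency. It leaves a gap of up to 30 days without a classification and gives two tests for worsening. It does not show that pre-dose illness is charged to the vaccine.

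**What to change.** **SAP 9.3.1.** Keep Tables 20–28 and Table 24 as planned. Beside them, for each dose and symptom, add the number and percentage of subjects whose maximum post-dose grade exceeds the grade at that dose's own pre-injection assessment. Report both counts when describing reactogenicity. State that the comparator is the score for that dose, since SAP 3.3 names only Day 1. State also whether injection-site symptoms are scored before dosing, so that the text and Table 29 agree.

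**Protocol 8.1.1, SAP 3.3 and SAP 9.** Define the AE baseline as the subject's state before the first study product injection, so that a condition starting after screening but before dose 1 is medical history. Use one worsening rule in all three places.

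**Cost.** One derived flag, one extra set of columns and wording changes in three places. Scores already collected suffice for systemic symptoms, and for injection-site symptoms if these are confirmed as scored before dosing. The supplementary count can miss a reaction that recurs or is prolonged at the same grade; showing both counts keeps that visible.
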